6.2 Safety Outcomes (H7)

Safety outcomes to be considered in the analysis will include the following:

- Seizures, clinical and/or EEG
- Excessive stool output
- Respiratory disturbance
- Feeding intolerance

6.3 Secondary Outcomes

Secondary outcomes that will be considered during initial analysis will include but not limited to:

• Number of days on morphine from first weaning dose to cessation of opioid for slow- and rapid-wean groups (H2)

- Number of days on methadone from first weaning dose to cessation of opioid for slowand rapid-wean groups (H3)
- Escalation or resumption of opioid during treatment (Y/N scenario)) (H4)
- Total amount of opioid from first weaning dose to cessation of opioid for non-withdrawn infants (H5)
- Initiation and/or escalation of second- or third- line drugs to treat NOWS signs from the first weaning dose to cessation (H6)
- Atypical neurobehavioral profile prior to discharge using the NICU Network Neurobehavioral Scale (NNNS)(H8)
- Length of hospital stay (H9)
- Maternal well-being measured using PROMIS, one month post discharge and at 24-month follow-up visit (H10)
- Maternal-infant attachment measured using MPAQ total scores, one month post discharge (H10)
 - o Maternal well-being
 - o maternal-infant attachment
- Infant growth (H11)
 - o Weight, height, head circumference at 24-month follow-up visit
- Infant wellness after discharge and initial 24 months of age looking at ER and acute care facility visits over time (Y/N for time (1-4)) (H12)
- BISTEA consists of two multi-item scales, a problem scale (31 items) and competence scale (11 items), with high score on the problem scale or a low score on the competence scale being less favorable. (H12). These scores will be converted to percentiles based on BITSEA Examiner's Manual (BITSEA ph2 Manual MapiTrust.pdf)
- Infant development to 24 months of age (H13)
 - o Bayley cognitive, language, and motor performed by a developmental specialist.

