4.3 Analysis Datasets

The analyses for each outcome will be performed using an intention-to-treat (ITT) framework, defined as the inclusion of all infants randomized and consented into the study and analyzed according to the trial arm to which the infant was randomized to.

5 Trial Population

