5.2 Withdrawal / Follow-up

Caregiver of infants withdrawn from the study will be given three options: 1. Discontinuation of study intervention with permission to continue study specific assessment and data collection, 2. Withdrawn with permission to continue data collection per protocol, or 3. Withdrawn with discontinuation of further data collection. If withdrawal status allows for continued data collection, then information about the number of days infants were treated for NOWS with opioids after withdrawal from the intervention will be collected.

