5.3 Analysis Populations

The Full Analysis Set (FAS)¹ population will serve as the population for the analysis of efficacy data in this trial. The FAS population consists of all subjects randomly assigned to treatment who completed the treatment, this will include non-withdrawn infants as well as withdrawn infants with permission for continued data collection.

Survival analysis and safety analysis will utilize Intention-to-treat population, defined as the inclusion of all randomized participants. For the survival analysis, efficacy outcome for withdrawn infants with discontinuation of further data collected will be right censored.

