6.4 Frequentist Statistical Methods

6.4.1 Statistical Methods

The proposed analyses will be conducted using the intent to treat (ITT) population.

Consort Diagram

Patient accounting will be presented in a consort diagram. This diagram will include:

- Number of infants screened
- Number of infants eligible
- Number of infants consented
- Number of infants randomized
- Number of infants randomized by group
- Number of infants in each medication category
- Number of infants with primary outcome per group per medication

Descriptive Tables

Baseline characteristics and outcomes will be descriptively summarized in the following manner:

Binary (yes/no, 1/0 type) measures will be summarized by level with frequency out of the total non-missing values and percentage of total non-missing values. Percentages will be reported to one decimal place, nn(XX.X%) or nn/NN(XX.X%)

Multiple level discrete measures will be tabulated with one row per level and with a row indicating how many observations had missing data. Percentages will be calculated as percent of all observations associated with a given treatment.

Continuous measures will be summarized by number of non-missing values, means and standard deviation [n: XX.X (XX.X)], or by median with minimum and maximum, or by median with first and third quartile [n: XX.X (XX.X , XX.X)]. Mean, standard deviations, median, minimum, maximum, and quartiles will be reported to one decimal place.

Count data will be summarized using median (min, max).

Statistical Modeling and Inferences

Statistical modeling will be performed using linear mixed model for continuous measures and generalized linear mixed model for binary and count outcomes with logit and log link functions, respectively. All models will include site as random effect and intervention arm as a fixed effect. Secondary outcome models will also be adjusted for maternal treatment, stabilization dose, and breast feeding.

For the ith infant, all models (except the primary) will have the following form $g(\mu_i)$ with g(.) being a monotonic link function and the following form:

```
g(\mu_i) = \beta_o + \beta_1 I(\text{intervention=fast}) + \beta_2 I(\text{Maternal Treatment=methadone}) + \beta_3 I(\text{Materna Treatment= Buprenorphine } \pm \text{ naloxone}) + \beta_4 I(\text{Maternal Treatment=other opioids}) + \beta_5 (\text{stabilization dose}) + \beta_6 (\text{Maternal feed=Yes}) + \beta_i X_i
```

where:

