6.4.4 Subgroup Analysis

For the primary outcome the following subgroup analyses will be performed:

- 1. By race/ethnicity
- 2. By sex

Each model will be similar to the analysis described in section 6.4.1 but will also include fixed effect for the stratification variable as well as an interaction between intervention and the stratification variable. If

p-value for interaction is less than 0.10 then we will report the treatment effect within the specified subgroup. We will not correct for multiple testing as all analyses other than the primary are considered exploratory.

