6.4.5 Sensitivity Analysis

Because of censoring and/or partial data collected on withdrawn infants we will perform the following additional analyses:

- 1. Replicate the primary analysis (H1) to include maternal treatment, stabilization dose, and maternal feeding.
- 2. Given the learning curves needed to be successful at this trial, we will run a sensitivity analysis limited to centers that enrolled greater than 10 infants.
- 3. Replicate the primary outcome analysis to evaluate the effect of being part of Eat Sleep Console
- 4. Perform survival analysis using cutoff at 35 days as censoring indicator.
- 5. If sample size allows, competing risk analysis will be performed using Cox proportional hazard model adjusting for the following: parental withdrawal, physician withdrawal, and treatment failure defined as unable to wean by 35 days of methadone/morphine treatment. This analysis will allow for additional inquiry into the intervention effect on the primary outcome while accounting for competing safety and withdrawal risks.
- 6. For H13, perform a sensitivity analysis for all hypotheses by removing follow ups outside the 22-26 weeks window.

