6.6 Missing Data

6.6.1 In-hospital data

Analysis will be completed on the ITT principle, so data will be analyzed as randomized. No imputation for missing outcome data is planned, so the analysis will be based on the Full Analysis Set.

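### H5 (total opioid) is restricted to non-withdrawn infants against the SAP's own analysis sets, without a stated reason or sensitivity analysis, and pools two drugs with no stated unit or drug term

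*SAP*

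**What the plan says.** **Analysis set.** The H5 entry in SAP 6.3 reads "Total amount of opioid from first weaning dose to cessation of opioid for non-withdrawn infants (H5". Four other sections point to a wider set:

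- SAP 4.3: "The analyses for each outcome will be performed using an intention-to-treat (ITT) framework", covering all randomised and consented infants.
- SAP 6.4.1: "The proposed analyses will be conducted using the intent to treat (ITT) population".
- SAP 5.3: efficacy uses a full analysis set (FAS) of randomised subjects "who completed the treatment, this will include non-withdrawn infants as well as withdrawn infants with permission for continued data collection".
- SAP 6.6.1: "No imputation for missing outcome data is planned, so the analysis will be based on the Full Analysis Set".

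Protocol 5.1.5 analyses total opioid like the primary outcome, which Protocol 5.1.4 puts on an intention-to-treat basis.

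**Withdrawn infants.** SAP 5.2 offers caregivers three options. Two allow data collection to continue; the third is "Withdrawn with discontinuation of further data collection". For the primary outcome, SAP 6.1.1 keeps infants under the first two options by adding their opioid days after withdrawal (form Weaning12, Q5b). SAP 6.4.5 opens with "Because of censoring and/or partial data collected on withdrawn infants we will perform the following additional analyses". Its items 1 to 5 concern the primary outcome and item 6 concerns H13.

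**Scale.** SAP 2.2.1 tests H5 across both drugs together, and SAP 4.1 uses one linear mixed model with site as a random effect. The named covariates (SAP 6.4.1, 6.4.3) are maternal treatment, stabilization dose and breastfeeding. The endpoint in Protocol Table 1 carries no unit.

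**The concern.** Restricting H5 to non-withdrawn infants conditions on an event after randomisation. Under Protocol 4.2.6 an infant may leave the intervention after a serious adverse event, or on the clinical team's or parents' decision. Such events may relate both to assigned arm and to opioid need. Days of treatment and total opioid are two views of the same exposure, yet the first would include infants that the second drops.

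The boundary of the restricted set is also unclear. Infants who exit at day 35 stay in the trial under Protocol 4.2.6, and the SAP does not say whether they, or infants who exit for other reasons, count as withdrawn for H5. If day-35 exits count, the longest-treated infants are lost.

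On scale, a milligram of morphine and a milligram of methadone enter one outcome. The pooled difference is then a weighted mixture whose value changes with the share of infants on each drug, and Protocol 1.4 lets hospitals change drug during the trial.

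**Working it through.** The plan states no expected value, SD or power for H5, so there is no figure of its own to reproduce. The checks below illustrate size.

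**1. Difference by drug.** Inputs are the dose tables in Protocol Appendices 4–7 (3.2 kg infant), taking one day per dose level and no escalation. Total = sum of active dose levels × doses per day.

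| Example | Rapid, mg | Slow, mg |
|---|---|---|
| Morphine every 3 h | 0.53 × 8 = 4.24 | 0.84 × 8 = 6.72 |
| Morphine every 4 h | 0.71 × 6 = 4.26 | 1.14 × 6 = 6.84 |
| Methadone every 8 h | 0.88 × 3 = 2.64 | 1.41 × 3 = 4.23 |
| Methadone every 12 h | 1.32 × 2 = 2.64 | 2.11 × 2 = 4.22 |

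Averaged over the two intervals, slow minus rapid is:

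- Morphine: 6.78 − 4.25 = 2.53 mg, or 2.53 / 3.2 = 0.79 mg/kg.
- Methadone: 4.225 − 2.64 = 1.585 mg, about 1.59 mg, or 0.50 mg/kg.

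**2. Pooled difference.**

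- 70% morphine (Protocol 5.2.3): 0.70 × 2.53 + 0.30 × 1.585 = 2.25 mg.
- 87% morphine (Protocol 3.3.2): 0.87 × 2.53 + 0.13 × 1.585 = 2.41 mg.

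**3. The same contrast in stabilization-days.** From Protocol Table 4, as multiples of the infant's own daily stabilization dose:

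- Rapid: 0.85 + 0.70 + 0.55 + 0.40 + 0.25 = 2.75.
- Slow: 0.90 + 0.80 + 0.70 + 0.60 + 0.50 + 0.40 + 0.30 + 0.20 = 4.40.
- Difference: 1.65 for either drug.

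So the drugs differ here only through the size of the daily dose.

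**4. Unit of the dose covariate.** Protocol 4.2.6 gives stabilization dose in mg/kg/day and Appendix 8 in mg/kg/dose. In the Appendix 4–7 examples:

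- Per day, morphine is higher: 0.06 × 8 = 0.08 × 6 = 0.48, against 0.10 × 3 = 0.15 × 2 = 0.30 mg/kg.
- Per dose, morphine is lower: 0.06–0.08 against 0.10–0.15 mg/kg.

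The unit reverses the ordering of the drugs, so it affects how well the covariate can stand in for drug.

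**5. Effect of dropping withdrawn infants.** The documents give no withdrawal rate, so every rate here is assumed. Let wR and wS be the proportions withdrawn in the rapid and slow arms, and let withdrawn infants receive k times their own arm's total, with k = 0.5 or 1.5.

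All-infant difference = 4.40 × [1 + wS(k − 1)] − 2.75 × [1 + wR(k − 1)], against 1.65 in non-withdrawn infants.

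| wR | wS | k = 0.5 | k = 1.5 |
|---|---|---|---|
| 5% | 5% | 1.61 | 1.69 |
| 20% | 20% | 1.49 | 1.82 |
| 15% | 5% | 4.290 − 2.544 = 1.75 | 4.510 − 2.956 = 1.55 |
| 5% | 15% | 4.070 − 2.681 = 1.39 | 4.730 − 2.819 = 1.91 |

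With unequal withdrawal the shift is about 6% (1.75 / 1.65) when the rapid arm loses more and about 16% (1.91 / 1.65) when the slow arm does. It can go either way.

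**The case against.** The restriction looks like a data limit rather than a selective choice. The only post-withdrawal opioid field that SAP 6.1.1 names counts days, not amounts. Without a dose, total opioid is missing after exit, and with no imputation planned a complete-case rule for this outcome follows. The general sections also disagree among themselves, ITT in two and FAS in two. All of this stands and makes the restriction understandable. It does not supply the missing reason, define who counts as withdrawn, or give H5 a sensitivity analysis.

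On scale, opioid choice follows hospital practice (Protocol 4.2.6), so the site random effect takes up part of the between-drug variance, and stabilization dose may take up more. That stands too; what remains comes from hospitals that change or mix drugs. The open covariate term in SAP 6.4.1 does not settle the matter, since 6.4.3 admits extra covariates only for substantial imbalance and if sample size allows. A unit may appear in the table shells or the separate outcome-calculation file, which are not part of the text reviewed.

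An obvious remedy, carrying the last dose forward as the main analysis, is open to fair objection. It reverses SAP 6.6.1 and ignores changes of dose, route or drug after exit. It also writes the assigned schedule into off-protocol exposure: at step 4 without escalation the arms stand at 40% and 60% of the stabilization dose. It belongs in a sensitivity analysis only.

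**Conclusion.** The H5 set in SAP 6.3 conflicts with 4.3, 5.3, 6.4.1 and 6.6.1, is unexplained, and has no sensitivity analysis. H5 therefore rests on a selected set that differs from the set for days of treatment. Separately, its pooled milligram difference has no fixed meaning without a unit and a drug term: 2.25 to 2.41 mg at 70% to 87% morphine, around drug-specific values of 2.53 and 1.59 mg. These are protocol examples, and Protocol 4.2.6 warns that actual doses will likely differ.

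A reader might infer more than the documents support:

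- That the restriction favours one arm. Without a withdrawal rate, neither size nor direction is known; the 6% and 16% shifts rest on assumed inputs.
- That pooling invalidates the test. It does not: infants are on their drug before randomisation, and randomisation is within hospital. The cost is in interpretation and some precision.

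Priority is modest, because SAP 6.4.4 states that "all analyses other than the primary are considered exploratory".

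**What to change.** 1. **Drug and unit.** Add the infant's drug at randomisation (morphine or methadone) as a fixed effect in the H5 model and report H5 separately by drug. State the unit, for example mg/kg, and define the stabilization-dose covariate per kg per day. The drug, weight, interval and dose are already inputs to the dosing calculator (Protocol Appendix 8).

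2. **Analysis set.** Keep the non-withdrawn set as the main H5 analysis only if SAP 6.3 states the data limit and says whether day-35 and other exits count as withdrawn. Add a prespecified FAS sensitivity analysis: recorded opioid to exit, plus post-exit opioid days (Weaning12 Q5b) times an assumed daily dose. Vary that dose over a range, for example 0 to 2 times the last recorded non-zero daily dose, first equally and then differently by arm. Non-zero matters because three of the eight rapid-arm levels are placebo and no slow-arm level is. Label this an analysis assumption, not a treatment rule.

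3. **Wording.** Align SAP 4.3, 5.3, 6.3, 6.4.1 and 6.6.1 on the H5 set, with an exception in 6.6.1 for this sensitivity analysis. In 5.3, reconcile completion of treatment with the inclusion of withdrawn infants in the same sentence.

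The cost is a few extra model runs, one derived variable and SAP text. The post-exit dose is assumed, but only in the sensitivity analysis. If the added term causes convergence trouble, SAP 6.4.2 already allows covariates to be reduced, and the by-drug results remain.

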
 To determine whether a rapid- or slow-wean intervention among infants receiving an opioid (defined as morphine or methadone) as the primary treatment for neonatal opioid withdrawal syndrome (NOWS) affects maternal well-being and maternal infant attachment at four weeks (\pm 7 days) after discharge 	
 Parent-Reported Outcome Measure Information System (PROMIS) Measures at 1 month after discharge and at 24 months of age Maternal Post Attachment Questionnaire (MPAQ) at one month after discharge

 To determine whether a rapid- or slow-wean intervention among infants receiving an opioid (defined as morphine or methadone) as the primary treatment for neonatal opioid withdrawal syndrome (NOWS) affects growth over the first 24 months of age 	
 Weight (kg), length (cm), head circumference (cm), and weight for length percentile on the World Health Organization (WHO) growth curves. Anthropometric z-scores and BMI-z at 24 months of age

 To determine whether a rapid- or slow-wean intervention among infants receiving an opioid (defined as morphine or methadone) as the primary treatment for neonatal opioid withdrawal syndrome (NOWS) affects infant wellness after discharge and until 24 months of age 	
 Acute/urgent care and/or ER visits (total number of occurrences) (CQ) Readmissions (number of occurrences) (CQ) Death (presence or absence)

 To determine whether a rapid- or slow-wean intervention among infants receiving an opioid (defined as morphine or methadone) as the primary treatment for neonatal opioid withdrawal syndrome (NOWS) affects infant development. 	
 Bayley Scales of Infant and Toddler Development, Fourth Edition (Bayley 4): Cognitive, Language, Motor, at 24 months of age

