should be individualized, supportive, and non-pharmacologic (2). These measures should include minimizing environmental stimuli (e.g., rooming in [10]), encouraging breast-feeding (in the absence of contraindications), and providing sufficient caloric intake. Pharmacological therapy is indicated when signs of NOWS cannot be controlled with non-pharmacological strategies. The objective of pharmacological therapy is to control NOWS signs so that an infant can appropriately bond with her or his mother, tolerate handling and care by healthcare providers, eat effectively with appropriate rest periods to ensure adequate growth, and avoid serious central nervous system dysfunction, such as seizures. Clinical teams traditionally initiate drug treatment when scoring assessments reach a predetermined severity of NOWS signs and include three phases (initiation, stabilization, and weaning). Initiation is the start of drug treatment, and clinical teams progressively increase the dose until the infant achieves stabilization. Stabilization is the interval of time during which the clinical team maintains a drug dose that controls NOWS signs without any indication to further increase the dose. Weaning consists of serial reductions in drug dose and/or lengthening the time interval between doses, and it often begins approximately 48 hours after stabilization. NOWS treatment goals should address four domains: 1) support vital neonatal functions (nutrition, appropriate sleep patterns, etc.), 2) promote family bonding, 3) prevent complications (seizures, excessive weight loss, unmanageable irritability), and 4) provide education for the mother-infant dyad and integration into social services to facilitate a smooth transition out of the hospital (7).

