We will provide the mean and SD of infants' weights (z-scores) separately for each treatment group. We will use a mixed linear model to evaluate the effect of treatment arm on weight (z-scores). The model will examine how the treatment means differ (i.e., main treatment effect), how treatment means change over time (i.e., main time effect), and how differences between treatment means change over time (i.e., treatment-by-time effect). We will carry out assessment across 3 time points: birth, hospital discharge, and 24 months of age. The mixed model longitudinal analytical approach allows us to analyze correlated data obtained repeatedly from the same participant and account for the ICC among participants nested within with same clinical site. To account for potential imbalance in key demographic and site-level characteristics, unadjusted and adjusted GLMMs will be fit to the data. Initially, the unadjusted mixed model will include the fixed categorical effects of intervention, time, and intervention-by-time interaction and the random-site effect. We will calculate the point estimates and their respective CIs for the changes in infants' weights for each intervention group and for the difference in the estimated change between intervention groups. Additionally, the team will present the p-value of the difference in point estimates between intervention groups.

We will examine the impact of the treatment arm on length, HC, and infant weight for length (z-scores) using the same analytical methods described for weight (z-scores) above. Additionally, we will provide the mean and SD of infant BMI-z at 24-months for each treatment group. The team will use a GLMM with an identity link to compare average BMI-z between the groups, and the team will report point estimates for the group mean difference along with a 95% CI.

To compare Bayley-IV scores between intervention arms, we will perform a linear mixed-effects model with a fixed effect for the intervention group and a random effect for study site. We will report point estimates for the group mean difference along with a 95% CI, and the team will repeat this analytical approach for each of the Bayley-IV domains.

Descriptive statistics (means, medians, SD, percentiles) for continuous secondary outcomes and frequency based statistics (N and percentages) for binary secondary outcomes will be generated and summarized in a tabular form by treatment group.

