 - D) **Objective 7.d**: To compare the proportion of infants in each intervention arm with feeding intolerance

Additional secondary objectives

8) **Research Objective 8**: To compare infants in each treatment arm with an atypical neurobehavioral profile prior to discharge on the NICU Network Neurobehavioral Scale (NNNS).

H₀: Behavioral profiles will not differ between rapid- and slow-wean treatment regardless of medication used.

H_a: Behavioral profiles will differ between rapid- and slow-wean treatment regardless of medication used.

9) **Research Objective 9**: To compare the lengths of hospital-stay between the treatment intervention arms. Specifically, we expect that the length of hospital stay will be lower in the rapid-wean group then in the slow-wean group regardless of medication use.

H₀: The length of hospital stay will not differ between rapid- and slow-wean treatment regardless of medication used.

H_a: The length of hospital stay will differ between rapid- and slow-wean treatment regardless of medication used.

- 10) **Research Objective 10**: Compare the following assessments between rapid- and slow-wean groups:
 - Statistical Hypothesis 10A: To compare maternal well-being using PROMIS score at 24-month between rapid- and slow-wean groups regardless of medication used adjusting for PROMIS score at one month.

H₀: PROMIS score at 24-month will not differ between rapid- and slow-wean treatment regardless of medication used.

H_a: PROMIS score at 24-month will differ between rapid- and slow-wean treatment regardless of medication used.

• Statistical Hypothesis 10B: To compare maternal-infant attachment measured using MPAQ total scores at one month post discharge

H₀: MPAQ total scores will not differ between rapid- and slow-wean treatment regardless of medication used.

H_a: MPAQ total scores will differ between rapid- and slow-wean treatment regardless of medication used.

- 11) **Research Objective 11**: To compare the growth over the first 24 months of age in each intervention arm.
 - Statistical Hypothesis 11A: To compare the weight z-score between rapid- and slow-wean groups regardless of medication used.

H₀: Infants z-scores for weights will not differ between rapid- and slow-wean treatment regardless of medication used.

H_a: Infants z-scores for weights will differ between rapid- and slow-wean treatment regardless of medication used.

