4.1 Modeling Process

For the primary outcome (H1), linear mixed model with site as random effect and intervention as a fixed effect will be used.

For safety outcomes, binomial proportions and their corresponding 95% CI by intervention arm for seizure (clinical and EEG), excessive stool output, respiratory disturbances, and feeding intolerance will be reported. Chi-square/Fisher exact tests will be used to compare between the intervention arms. If we end up with a very small number of adverse events and severe adverse events, analysis of these measures will be descriptive only.

For the secondary linear outcomes (H2, H3, H5 & H12d), linear mixed model with site as random effect will be used. For secondary binary outcomes (H4, H6), generalized linear mixed model with site as random effect will be used. For count outcomes (H12a-12c), generalized linear mixed models using either Poisson or negative binomial distribution and site as random effect will be used. Intervention will be included in the models as a fixed effect. Secondary outcome models will be adjusted for breastfeeding status, maternal treatment, and stabilization dose.

Hypotheses H9 – H11 will be analyzed in a similar manner to H2. For the PROMIS model (H10), we will adjust for 1-month after discharge and if mother is the primary care giver as fixed effect covariates.

Hypothesis H8 will be analyzed using latent profile analysis as specified in Liu et al. (2). Model fit indices and likelihood ratio tests will inform the determination for the most-appropriate number of classes.

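### The SAP does not carry forward, or justify dropping, the protocol's longitudinal growth analysis (birth, discharge, 24 months) or its weight-for-length and BMI-z comparisons

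*SAP*

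**What the plan says.** **SAP.** Objective 11 in section 2.2.1 is "To compare the growth over the first 24 months of age in each intervention arm". Hypotheses 11A to 11C cover weight, height and head circumference z-scores and name no time point; for weight, the null is "Infants z-scores for weights will not differ between rapid- and slow-wean treatment regardless of medication used". Section 4.1 gives the model in one line: "Hypotheses H9 – H11 will be analyzed in a similar manner to H2". H2 is a single-time outcome, analysed by a linear mixed model with site as the random effect. The general equation in section 6.4.1 has terms for arm, maternal treatment, stabilization dose, breastfeeding and further covariates. It names no time or treatment-by-time term. Section 6.3 is the only place that fixes a time for growth: "Weight, height, head circumference at 24-month follow-up visit". The SAP nowhere mentions discharge anthropometry, weight-for-length or BMI-z.

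**Protocol.** Table 1 (section 1.7) lists weight, length, head circumference and weight-for-length, and adds "Anthropometric z-scores and BMI-z at 24 months of age". Section 5.1.5 describes a mixed model for weight z-score with arm, time and arm-by-time effects: "We will carry out assessment across 3 time points: birth, hospital discharge, and 24 months of age". It applies the same method to length, head circumference and weight-for-length, and compares mean BMI-z between arms at 24 months.

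**The concern.** The two documents give different analyses for one secondary endpoint, and the SAP also falls short of its own objective: a single comparison at 24 months does not describe growth over the period. Of the three measurement times, discharge is the one closest to the intervention. Protocol 4.2.11 accepts that rapid weaning could increase withdrawal signs. The treatment goals in protocol 3.3.2 include to "prevent complications (seizures, excessive weight loss, unmanageable irritability". None of the four H7 safety outcomes measures weight, and the nearest, feeding, is recorded as a change in feeding strategy (protocol 4.2.12).

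Three things are at stake. A protocol-specified comparison near the intervention has no SAP specification. Two listed measures may go unreported. And with two analyses on paper, the choice between them could be made after the data are seen.

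**Working it through.** The point turns mainly on the texts, so they are set side by side first.

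| Element | Protocol 5.1.5 | SAP 2.2.1, 4.1, 6.3, 6.4.1 |
|---|---|---|
| Weight, length/height, head circumference | Yes | Yes |
| Weight-for-length | Yes, same method as weight | Not mentioned |
| BMI-z, 24 months | Yes, between-arm comparison | Not mentioned |
| Times | Birth, discharge, 24 months | 24 months (6.3); none named elsewhere for H11 |
| Time and arm-by-time terms | Yes | None named |
| Random effects named | Site; the text also says correlation within participant is handled | Site only |

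Version differences do not explain this. The SAP cites protocol version 10, and the protocol's change log from version 10 to 11 lists only face-page items. The SAP revision history (1.3) records a section on missing follow-up data and a wording change to the Bayley tables, and nothing on growth.

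**Precision at the two times.** Neither document gives a figure to reproduce for growth, so this is illustrative.

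Inputs:
- N = 302, the revised enrolment target in SAP 3.4. The number actually enrolled is not given.
- Discharge data near-complete: assumed.
- z-score SD of 1.0, with 1.2 as a second value, the same at both times: assumed.
- 24-month follow-up of 60%, the minimum in the Bayley power statement of protocol 5.2.3, and 80% as a more favourable assumption.

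For equal arms, ignoring site and covariates, the 95% CI half-width is 1.96 × SD × 2/√N.

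- Discharge, N = 302: 1.96 × 2/√302 = 0.226 (SD 1.2: 0.271).
- 24 months at 80%, 0.80 × 302 ≈ 242: 1.96 × 2/√242 = 0.252 (SD 1.2: 0.302).
- 24 months at 60%, 0.60 × 302 ≈ 181: 1.96 × 2/√181 = 0.291 (SD 1.2: 0.350).

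The ratio to discharge is 1/√(follow-up proportion): 1/√0.80 = 1.12 and 1/√0.60 = 1.29. With equal SD at both times it depends only on retention, so it does not change if enrolment ended below 302.

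**The case against.** The strongest reply is that nothing has been withdrawn. Protocol 5.1.5 still prespecifies the longitudinal model and the weight-for-length and BMI-z comparisons. The SAP list opens with "Secondary outcomes that will be considered during initial analysis will include but not limited to", so it is not exhaustive. Hypotheses 11A to 11C name no time, and the model equation leaves room for added covariates. Protocol 5.1.3 includes infant characteristics at the start of the intervention and at readiness for discharge among its descriptive data, and the SAP plans in-hospital tables whose contents are not in the text supplied.

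This defeats stronger readings that a reader might infer:
- That discharge growth will never be compared, or that no in-hospital growth effect can be seen. The documents show only that the SAP does not specify the comparison.
- That the SAP confines growth to 24 months throughout. Only section 6.3 names that time.
- That protocol Table 1 sets the three times. Only section 5.1.5 does.
- That leaving out BMI-z hides an in-hospital effect. BMI-z is a 24-month endpoint in the protocol too, so its absence is a reporting gap.
- That a growth deficit would show at discharge and fade by 24 months. Neither document supports this. Both arms allow escalation if signs recur, and a wider interval does not by itself show lost sensitivity without an effect size at each time.

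The reply does not remove the discrepancy. An open-ended list permits extra analyses but does not prespecify them. The SAP presents itself as the detailed plan for these objectives (section 3), and the model it assigns to H11 conflicts with the protocol's. Its silence cannot safely be read as retention, because it departs from the protocol elsewhere: its primary model omits maternal treatment and stabilization dose, which protocol 5.1.4 includes.

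It is also fair that growth is one of many secondary outcomes, that SAP 6.4.4 treats everything beyond the primary as exploratory, and that SAP 6.6.2 plans for missing follow-up data. These limit the weight of the point.

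**Conclusion.** The discrepancy holds. The SAP neither carries forward nor justifies dropping the protocol's growth analysis, and as written it does not answer its own Objective 11. Under the SAP's specification there is no between-arm comparison at discharge, and two protocol measures have no analysis.

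The 24-month comparison that remains has a CI about 12% wider than discharge would give at 80% follow-up and 29% wider at 60%. These figures assume near-complete discharge data and equal SD at both times. The 60% is the lowest value in a conditional power statement for the Bayley, not a forecast, so 29% belongs at the unfavourable end of the range. The textual finding needs none of these assumptions.

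The primary result and the listed safety outcomes are unaffected. This is a change the sponsor should make, on a secondary endpoint.

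**What to change.** In SAP 2.2.1 (H11), 4.1 and 6.3:

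- Restore the protocol 5.1.5 analysis for weight, length, head circumference and weight-for-length z-scores, with time and arm-by-time terms.
- Treat birth as the pre-randomisation value. If it is averaged into a treatment main effect, it dilutes any arm difference.
- Name a within-infant repeated-measures term alongside the random site effect.
- Report the arm contrasts at discharge and at 24 months separately. The discharge contrast belongs in the first-phase analysis; the 24-month contrast waits for the follow-up phase that SAP 3.7 places in July 2026.
- Use age-specific z-scores throughout, because age at discharge may differ by arm: H9 expects a shorter stay with rapid weaning.
- Restore the BMI-z comparison at 24 months.

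If any of these is deliberately dropped, the SAP should say so and give the reason. The cost is SAP wording and a few additional models on measurements already scheduled. The small downside is more exploratory contrasts, which should be labelled as such.
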